## 6.2 Study Rationale

The following sections highlight the rationale for the major components of this protocol.

### 6.2.1 Clinical Development Program for GS010

GS010 is being developed for the treatment of vision loss in LHON due to the G11778A *ND4* mitochondrial mutation. The clinical development of GS010 has included:

- Safety and tolerability study with dose-exploration

GS-LHON-CLIN-01: A Phase I/II, open label, dose-escalation safety and tolerability study. The maximal well-tolerated dose of [REDACTED] [REDACTED] per eye was selected for further study.

- Unilateral administration efficacy study in subjects with vision loss up to six months

GS-LHON-CLIN-03A RESCUE: A Phase III randomized, sham-controlled, GS010 (dose [REDACTED]) administration study in subjects with vision loss for up to six months.

- Unilateral administration efficacy study in subjects with vision loss for more than six months and up to 1 year

GS-LHON-CLIN-03B REVERSE: A Phase III randomized, sham-controlled, GS010 (dose [REDACTED]) administration study in subjects with vision loss for more than six months and up to 1 year.

LHON is a bilateral disease. Often the eyes of a given subject are affected sequentially and potentially the elapsed time between onset of vision loss and treatment administration may impact the presence and magnitude of the treatment effect in a neurodegenerative disease such as LHON. As such, the next step in the clinical development plan for GS010 is to assess the safety and efficacy of bilateral administration of intravitreal GS010 and to determine if a difference exists in the treatment of the first- and second-affected or not-yet-affected eyes.

Recent GS010 study results have shown that the benefit from GS010 is more pronounced after 1-year post injection. Preliminary data from the REVERSE study demonstrated that there is an improvement from baseline in BCVA at Week 72 of +15 ETDRS letters ( $-0.295$  [Standard Error  $\pm 0.063$ ] LogMAR;  $p < 0.0001$ ) and of +12 ETDRS letters ( $-0.246$  [Standard Error  $\pm 0.063$ ] LogMAR;  $p = 0.0003$ ) in GS010 treated eyes and sham treated eyes, respectively (data on file). This improvement in BCVA was less marked at Week 48 with +11 letters and +10 letters in GS010 treated eyes and sham eyes, respectively (data on file). This sustained and increased improvement in BCVA over time supports a read out of the primary endpoint in the REFLECT study at 1.5 year-post treatment.

### 6.2.2 Selection of the Primary Eye for Comparison and Randomization Scheme

LHON is a neurodegenerative disease with apoptotic neuronal cell death of the RGC. Structural imaging with Optical Coherence Tomography has revealed a progressive loss of the Ganglion Cell Layer (GCL) and Retinal Nerve Fiber Layer (RNFL), commencing in the pre-symptomatic stage through the acute and sub-acute stages of vision loss (Barboni 2010, Balducci 2016, Hedges 2016, Moster 2016).

The bilateral nature and common manifestation of sequential onset of vision loss have also enabled a unique opportunity to study investigational therapeutics in LHON. The paradigm of therapeutic intervention prior to clinically manifested vision loss in the second eye to be affected has been recommended as powerful method of proving therapeutic effectiveness in LHON (Newman 2005). Lam and colleagues (Lam 2010, Lam 2014) are developing an alternative vector for gene delivery in LHON *ND4* and recommend that efficacy should be proven in recently affected subjects with Snellen visual acuity of better than 20/40 in one eye and worse than 20/40 in the fellow eye, with active treatment administered to the better seeing eye. Klopstock and colleagues (Klopstock 2011) performed a randomized controlled trial of idebenone (Raxone®) and although the study failed to reach its primary endpoint, a trend of response was noted in subjects with discordant visual acuities, in essence, those subjects with relatively preserved visual acuity in one eye and loss of visual acuity in the other eye.

In this study protocol, the eye selected for primary analysis is the second affected/not yet affected eye. The study design will also allow assessment of the presence of a difference in treatment effect in first affected and secondly affected/not yet affected eyes, with an intra-subject comparison.

Subjects will be randomized to one of two treatment arms. In both treatment arms, the first affected eyes will receive intravitreal GS010. The two arms differ in that secondly affected/not yet affected eyes will receive intravitreal GS010 in one treatment arm and in the other treatment arm, secondly affected/not yet affected eyes will receive a placebo intravitreal injection. When subjects report simultaneous onset of vision loss in both of their eyes, indicating that the subject was unable to distinguish which is the first affected eye and which is the second affected/not yet affected eye, the second affected/not yet affected eye will be chosen randomly to minimize bias.

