### 7.2 Secondary Objective(s)

The efficacy objectives listed below will be analyzed for the second affected/not yet affected eyes as the main eye of interest (designated the primary eye). Exploratory efficacy analyses will also be conducted for the first affected eyes, but those analyses are secondary to any analysis for the primary eye which is the second affected/not yet affected eye.

1. To assess the safety and tolerability of bilateral and unilateral intravitreal injection of GS010.
2. To compare the time course of the BCVA LogMAR response in second affected/not yet affected eyes treated with GS010 compared to placebo treatment.
3. To assess, at 1.5 years, 2, 3, 4 and 5 years post-treatment, the efficacy of intravitreal GS010 compared to placebo intravitreal injection in second affected/not yet affected eyes, by determining the difference in the rate of responder eyes.
4. To compare the time course of the response in second affected/not yet affected eyes treated with GS010 compared to placebo treatment and to estimate the magnitude of the treatment effect at 1.5 years, 2, 3, 4 and 5 years post-treatment, with parameters measured by:
  - a. SD-OCT;
  - b. HVF 30-2;
  - c. Pelli-Robson Low Vision Contrast Sensitivity.
5. To verify whether a difference exists at 1.5 years 2, 3, 4 and 5 years post-treatment, between first affected eyes and second affected/not yet affected eyes treated with GS010, using both an intra-subject and inter-subject analysis, with
  - a. LogMAR BCVA
  - b. Parameters measured by SD-OCT
  - c. Parameters measured by HVF 30-2, and
  - d. Parameters measured with Pelli Robson Low Vision Contrast Sensitivity.
6. To assess, at 1.5 years, 2, 3, 4 and 5 years post-treatment, the rate of responders in first affected eyes treated with GS010.
7. To assess humoral and cellular immune responses to AAV2 after unilateral and bilateral intravitreal administration.
8. To assess the impact of bilateral intravitreal GS010 administration on QoL scales at 1.5, 2, 3, 4 and 5 years post-treatment.

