An Interactive Response System (IRS) will assign a unique subject identification number at Screening Visit (Visit 1), which will be required for all communication between the Investigator (or designee) and the IRS. Subject numbers will be tracked via the IRS. The IRS will be used to enroll and randomize subjects based on a pre-defined central randomization scheme. An IRS User Guide will describe all steps for enrollment and randomization of subjects.

Subjects meeting all eligibility criteria for selection and inclusion will be randomized to treatment arm 1 (TARM1) or treatment arm 2 (TARM2) in a 1:1 allocation (see Figure 1). Subjects in TARM1 will receive intravitreal GS010 in their first affected eye and their second affected/not yet affected eye. Subjects in TARM2 will receive intravitreal GS010 in their first affected eye and placebo intravitreal injection in their second affected/not yet affected eye. For subjects who report simultaneous onset of vision loss in both eyes, the right or left eye will be selected randomly to serve as the second affected/not yet affected eye. If the right eye is selected randomly as the second affected/not yet affected eye, the left eye will be designated as the first affected eye, and vice versa.

Figure 1: Post-Treatment Follow-up Period 1: up to 2 years post-treatment

Administration of an IOP lowering agent of the investigator's choice will precede all intravitreal injections. Pre-intravitreal injection procedural preparation will include pupil dilation, topical antisepsis, and topical anesthesia. The IMPs (GS010 and placebo) will be administered with a standard intravitreal injection procedure. Each eye will undergo administration of the allocated treatment with a single intravitreal injection, performed as a separate procedure. Please refer to the Intravitreal GS010/Placebo Injection Guide for full details.

Per the Investigator's discretion and according to local standard accepted medical practices, treatment administration to both eyes may be performed at a single Treatment Visit (Visit 3) (i.e. intravitreal injection of both eyes of a given subject is performed the same day as two separate procedures) or may be performed on two consecutive days (i.e. one eye of the subject will be administered the allocated treatment one day and the next day the fellow eye of the subject will be administered the allocated treatment).

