### 13.10.1 Determination of the Best- and Worst-Seeing Eye

At Inclusion Visit (Visit 2), the best-seeing and worst-seeing eyes of each subject will be determined, based on the baseline vision testing performed at Visit 2. This will allow for assessment of the presence of a difference of the treatment effect in best- and worst-seeing eyes. A pre-defined algorithm for determining the best- and worst-seeing eyes will be utilized as follows:

1. LogMAR BCVA: On-chart eyes and off-chart eyes will have a LogMAR BCVA per the study's SOP for visual acuity testing. The eye of the subject with the better (i.e. lower or more negative) LogMAR BCVA will be the better-seeing eye of the subject. If both eyes have an equal LogMAR acuity the second criterion will be utilized.
2. SD-OCT parameters (to be used if there is no inter-eye difference based on Criterion 1):
  - i. The initial SD-OCT parameter will be the total volume of the RGC layer of the ETDRS macula area. The better-seeing eye will have the greater volume and quadrant thickness, unless there is macula edema. A difference of  $\geq 5\%$  is considered significant to determine greater volume.
  - ii. The second SD-OCT parameter (to be used if there is no inter-eye difference in criteria 2i) will be the combined volume of the RGC layer of the inner and outer nasal quadrants of the macula. The better-seeing eye will be the eye with greater volume. A difference of  $\geq 5\%$  is considered significant to determine greater volume.
3. Log of Contrast Sensitivity (LogCS) obtained with the Pelli Robson Low Vision Contrast Sensitivity Chart (to be used if there is no inter-eye difference in criteria 1 or 2). The eye with the best LogCS score is the better-seeing eye.
4. If the eyes are equal based on criteria 1 through 3, the best-seeing eye will be based on the subject's opinion.

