6.4. Examination of subgroups

Subgroups analyses will be performed. The following subgroups will be assessed for the primary endpoints (BCVA):

- Eyes on-chart for LogMAR BCVA at baseline,
- Eyes off-chart for LogMAR BCVA at baseline
- Pediatric (<18 years-old)/Adult populations,

- Males/Females,
- Previous idebenone treatment yes/no.

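### First eyes have no placebo control, so comparing first with second eyes cannot show a difference in treatment effect, and no planned analysis asks whether the effect varies with time since onset

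*Protocol*

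**What the plan says.** **Rationale.** Protocol 6.2.1 gives as a reason for the trial that "the elapsed time between onset of vision loss and treatment administration may impact the presence and magnitude of the treatment effect", and makes a comparison of first and second eyes part of the next development step.

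**Claimed property of the design.** Protocol 6.2.2 says the design will also "allow assessment of the presence of a difference in treatment effect in first affected and secondly affected/not yet affected eyes", by an intra-subject comparison. Protocol 13.10.1 makes a parallel claim for eyes classified by acuity at Visit 2: "This will allow for assessment of the presence of a difference of the treatment effect in best- and worst-seeing eyes".

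**Allocation.** "In both treatment arms, the first affected eyes will receive intravitreal GS010" (Protocol 6.2.2). Protocol 9.1 confirms where placebo is used: "Subjects in TARM2 will receive intravitreal GS010 in their first affected eye and placebo intravitreal injection in their second affected/not yet affected eye".

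**Objective 5.** Protocol 7.2 compares first "affected eyes and second affected/not yet affected eyes treated with GS010, using both an intra-subject and inter-subject analysis, with" LogMAR BCVA, SD-OCT, visual field and contrast sensitivity. SAP 2.2 repeats it. SAP 3.4, item 5, removes the intra-subject part, citing a regulatory recommendation against using the contralateral eye as a control.

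**Use of duration of vision loss.** In the protocol it is a covariate (16.4.1.8, 16.4.1.11, 16.4.2.4.2), and region is the only baseline factor with a planned treatment interaction (16.4.1.11, 16.4.2.1). In the SAP it is an adjustment or candidate covariate (13.1.5). The SAP 6.4 subgroups are on-chart and off-chart status, age group, sex and previous idebenone.

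**The concern.** A treatment effect needs a treated and an untreated outcome. For second eyes the trial has both, by randomisation. For first eyes it has only the treated outcome; by design no first eye gets placebo. A difference in change from baseline between GS010-treated first and second eyes therefore cannot be read as a difference in effect. First eyes are by definition at least as far into the disease as second eyes, and untreated course may depend on stage.

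At stake is any later statement on timing, for example that recently affected eyes benefit more. The documents supply no analysis that could support one. Yet data that bear on the question are collected: second eyes range from zero days to 365 days of vision loss (Protocol 9.1, 10.2.3) and are randomised to GS010 or placebo.

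**Working it through.** **1. What the contrast estimates.** Write E1, E2 for the GS010 effect in first and second eyes, and U1, U2 for mean untreated change. Then

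first minus second, both treated = (U1 + E1) − (U2 + E2) = (E1 − E2) + (U1 − U2).

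U2 is estimable from TARM2 second eyes. U1 is not estimable from any planned group. This holds within subjects (both eyes in TARM1) and between subjects (for example TARM2 first eyes against TARM1 second eyes).

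**2. Does change in treated eyes track effect?** The REVERSE figures in Protocol 6.2.1 (Week 72) are −0.295 LogMAR in GS010 eyes and −0.246 in sham eyes. The difference is 0.295 − 0.246 = 0.049, and 0.246/0.295 = 83% of the change in treated eyes also occurred in sham eyes. Change in treated eyes is a poor stand-in for effect.

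**3. How often the contrast would mislead.** Take E1 = E2, 45 subjects per arm and SD 0.50 (Protocol 16.2), with U1 − U2 assumed, since the documents do not give it.
- Between subjects: SE = 0.50 × √(2/45) = 0.105. A gap of 0.1 gives a significant result in about 16% of trials, and a gap of 0.2 in about 47%, against a nominal 5%.
- Within TARM1: SE = 0.50 × √(2(1 − ρ)/45), ρ assumed 0 to 0.7. A gap of 0.1 gives 15% to 40%; a gap of 0.2 gives 46% to 92%. The SAP no longer plans this version.

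**4. Is there another route to the question?**
- Repeating the primary analysis in first eyes (SAP 13.3) compares GS010 with GS010.
- The eye-level model in SAP 13.1.5 requests pooled GS010 eyes against placebo eyes, and GS010 eyes between arms. Neither is a first-versus-second estimate or involves duration.
- No treatment-by-duration term appears in either document.
- Best- and worst-seeing status returns in the SAP only as a baseline descriptor (section 9).

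**5. What the randomised second eyes could show.** First, the plan's own figure: n per arm = 2 × (1.960 + 0.842)² × 0.50²/0.30² = 43.6, so 44 by normal approximation. The noncentral t gives 45 with 80.4% power, matching Protocol 16.2.

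For a two-group modifier with share q of second eyes in one group, 45 per arm:

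SE = 0.50 × √[(2/45) × (1/q + 1/(1 − q))]

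| Modifier | q (assumed) | SE | 95% half-width | Power for 0.30 |
|---|---|---|---|---|
| Not yet affected | 0.10 | 0.35 | 0.69 | 13% |
| Not yet affected | 0.20 | 0.26 | 0.52 | 21% |
| Not yet affected | 0.30 | 0.23 | 0.45 | 26% |
| Duration, median split | 0.50 | 0.21 | 0.41 | 30% |

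At a median split the interaction detectable with 80% power is 0.59 LogMAR, and detecting 0.30 would need about 175 per arm. For continuous duration, SE = 2 × 0.50/√90 = 0.105 per SD. If the slope is fitted in affected eyes only, 90 becomes 90(1 − q), and the SE is 0.111, 0.118 or 0.126 per SD among affected eyes for q = 0.10, 0.20 or 0.30.

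**The case against.** The strongest reply is that the claim in 6.2.2 rests on an intra-subject comparison that SAP 3.4 deletes, and that SAP section 13 specifies no first-versus-second model. What remains would then be stale wording, not a misleading planned result. That stands as a limit on the consequence. It does not settle the point: the claim and objective 5 are still in force, the inter-subject form has the same missing control, and the reason given for the deletion concerns the contralateral eye as a control. The rationale question is left with no analysis.

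It is also fair that 6.2.2 speaks of allowing assessment, not of showing a difference; that objective 5 itself refers to GS010-treated eyes and does not mention effect; and that on-chart and off-chart subgroups are a rough proxy for severity. They are not time since onset.

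Two stronger readings are tempting.
- **A reader might infer that the trial will report a spurious first-versus-second difference of up to 0.30 LogMAR.** One can build 0.07 to 0.30 by assuming that 10% to 30% of second eyes are not yet affected and lose 0.7 to 1.0 LogMAR while first eyes stay put (0.10 × 0.7 to 0.30 × 1.0). The documents give neither that share nor the starting acuity. The figure is an unadjusted within-subject gap from an analysis the SAP has removed, and no change in first eyes sits badly with the −0.246 in REVERSE sham eyes.
- **A reader might infer that a treatment-by-duration term is an unbiased randomised test of treating earlier.** Treatment is randomised; duration is not. The term may reflect baseline acuity, age or anything else that travels with duration.

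**Conclusion.** The point holds as a mismatch between a stated property of the design and what the design can identify, with an unfilled gap in the analysis plan. That first eyes have no planned control, and that no analysis examines whether the GS010-placebo difference varies with time since onset, follows from the documents without assumptions. The false-positive rates depend on an assumed gap in untreated course and an assumed within-subject correlation. The interaction standard errors depend on the protocol's SD of 0.50 with 45 per arm, and on assumed shares of second eyes.

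The primary randomised comparison in second eyes and its alpha are untouched. The replacement analysis can give only a wide interval, at best about 30% power for a 0.30 interaction in the two-group splits examined, and can speak only to effect modification within the second-eye range of duration. That supports a cautious statement on timing, not a claim.

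**What to change.** 1. **Reword Protocol 6.2.2 and objective 5 (Protocol 7.2, SAP 2.2).** State that first-versus-second comparisons describe change from baseline in GS010-treated eyes and are not comparisons of treatment effect. Bring objective 5 into line with SAP 3.4, item 5.
2. **Add one exploratory model to SAP 6.4/13.1.5.** Start from the second-eye ITT ANCOVA of 13.1.4 and add affected/not-yet-affected status, time since onset among affected eyes, and the interaction of each with treatment. The status interaction is needed; without it, the estimate for not-yet-affected eyes is only the fitted line at day 0. Define status by zero days of vision loss (Protocol 9.1), not by the LogMAR cut-off that SAP section 9 uses for unilateral and bilateral status. Report GS010-placebo differences with 95% confidence intervals for not-yet-affected eyes and at a few durations, without a confirmatory test.
3. **Label it honestly.** The study is unmasked at 1.5 years (Protocol 13.11, SAP 13.1.2), and SAP version 10.0 dates from October 2024, after the 1.5-year analysis. State that the term was added after unmasking.
4. **Protocol 13.10.1.** Delete the claim, or add the matching exploratory term: treatment by whether the second eye is the best-seeing eye at Visit 2.

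The cost is wording and one or two extra fits on data already collected. The price in interpretation is low precision and a result that stays exploratory.

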### 6.2.3 GS010 Dose for Administration

The maximal, well-tolerated dose, as determined from the Phase I/II GS-LHON-CLIN-01 study, is [REDACTED]. This dose is being further studied in the unilateral administration Phase III studies RESCUE and REVERSE. It is intended to administer [REDACTED] in a final volume of [REDACTED] in this study.

### 6.2.4 Placebo Intravitreal Injection

This study includes a treatment arm (Treatment ARM2) in which each subject will receive intravitreal GS010 in their first affected eye and placebo intravitreal injection in their second affected/not yet affected eye. To appropriately mask subjects and the investigation team and minimize bias, a placebo intravitreal injection will be utilized. Please see Section 13.7.2 for a full description of the placebo injection.

### 6.2.5 Administration of an IOP lowering Agent Prior to Intravitreal Injection

IVT injection of therapeutic agents is associated with elevation of the IOP (Hollands 2007, Bakri 2009, Wu 2009, Frenkel 2010, Abedi 2013, El Chehab 2013, Kim 2013, Katayama 2014, Murray 2014, Dedania 2015). Data from ongoing clinical trials of intravitreal GS010 administration indicates that elevation of IOP is an expected potential side effect after intravitreal GS010 injection (please see refer to the Investigator's Brochure for additional details).

Use of pre-IVT injection IOP lowering agents has been shown by some groups to be effective in reducing the IOP elevation (Kim 2013). Others have recommended pre-treatment with IOP lowering agents in subjects whose optic nerve is at risk for further damage from transient or sustained IOP elevation, such as glaucoma subjects (Abedi 2013). By extension, the optic nerve of LHON subjects may be at higher risk for damage from transient or sustained IOP elevation, due to its already compromised status. Therefore, subjects will undergo administration of an investigator selected IOP lowering agent pre-IVT injection of GS010 and pre-IVT injection of placebo.

### 6.2.6 Administration of Immune Modulating Regimen

Immune responses to Adeno-associated virus (AAV) capsid proteins or the transgene product are reported to occur (Bennett 2003, Kumar-Singh 2008). Data in animal studies reveal a time- and

dose-dependent increase in neutralizing antibodies against AAV (MacLachlan 2011; Koilkonda 2014; Kotterman 2015). Several reports document ocular inflammation in pre-clinical studies of intravitreal AAV injection (MacLachlan 2011, Ye 2015, Ramachandran 2016).

GenSight-sponsored pre-clinical NHP studies of intravitreal GS010 also revealed the occurrence of ocular inflammation (Bouquet et al. in preparation). Thus, based on the available medical and scientific literature and the preclinical experience with intravitreal GS010, ocular inflammation is an expected adverse side effect of intravitreal GS010 injection. The occurrence of ocular inflammation after intravitreal injection of GS010 as a common ocular adverse side effect has also been noted in human clinical studies of GS010 to date. Please see the Investigator's Brochure for full details. To date, no trial of GS010 has been performed utilizing a peri-treatment immune modulating regimen.

Two other clinical programs are currently studying intravitreal AAV in subjects with vision loss due ND4 LHON. The first group (Wan 2016, Yang 2016) utilized oral corticosteroid immune modulation to prevent immune response and ocular inflammation and reported no ocular inflammation or any adverse events. The second group (Feuer 2016, Guy 2016 ARVO) reported preliminary results of a trial utilizing intravitreal self-complementary AAV, in which no immune modulation was utilized and noted the presence of low-grade ocular inflammation. This group had previously reported mild vitritis in a monkey (Koilkonda 2014).

Several ocular gene therapy studies have employed peri-treatment immune modulation to prevent ocular inflammation when administering intravitreal or sub-retinal AAV-based therapies (Bainbridge 2008, Hauswirth 2008, Maguire 2008, Cideciyan 2009, Maguire 2009, Bennett 2012, Jacobson 2012, MacLaren 2014, Bainbridge 2015, Rakoczy 2015).

Based on the medical and scientific literature noted above, preclinical NHP data for intravitreal GS010 injection, current experience in human clinical trials of GS010, and expert clinician recommendations, an immune-modulating regimen will be administered into subjects participating in this clinical trial. Please see sections 9 and 13.9.1 for additional details.

